9.7. Safety Evaluations

Safety and tolerability will be evaluated throughout the study from signing of the ICF onwards until the last study-related activity (end of study/early withdrawal).

An IDMC will be established for this study to monitor the safety of subjects. Details regarding the IDMC are provided in Section [11.12](#).

Any clinically relevant changes occurring during the study must be recorded in the AE section of the eCRF.

Any clinically significant abnormalities persisting at the end of the study/early withdrawal will be followed by the investigator until resolution or until a clinically stable endpoint is reached.

Safety assessments will be based on medical review of AE reports and the results of vital sign measurements, ECGs, physical examinations, clinical laboratory tests, and other safety evaluations at specified time points as described in the [Time and Events Schedule](#).

In the event that an invasive procedure such as a blood draw, mid-turbinate nasal swab, vital signs assessments, and/or ECG are required at the same time, the order of completion should be ECG first, then vital signs/SpO₂, then mid-turbinate nasal swab, then blood draw, with the mid-turbinate nasal swab and blood draw being obtained as close to the scheduled time as possible.

Adverse Events

Adverse events will be reported by the subject or the subject's legally acceptable representative for the duration of the study. Adverse events will be followed by the investigator as specified in Section 12.

Clinical Laboratory Tests

Blood samples for serum chemistry and hematology will be collected and analyzed by a local laboratory. The investigator must review the laboratory results, document this review, and record any clinically relevant changes occurring during the study in the AE section of the eCRF. The laboratory reports must be filed with the source documents.

The following tests will be performed by a local laboratory as initiation of treatment is time-critical:

Hematology Panel

-hemoglobin	Percentage and absolute counts of:
-hematocrit	-basophils
-mean corpuscular hemoglobin	-eosinophils
-mean corpuscular hemoglobin concentration	-lymphocytes
-platelet count	-monocytes
-red cell distribution width	-neutrophils
-reticulocytes	
-RBC count	
-white blood cell (WBC) count	

Serum Chemistry Panel

-alkaline phosphatase	-creatinine
-ALT	-creatinine kinase
-AST	-glucose
-bicarbonate (optional)	-potassium
-blood urea nitrogen	-sodium

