2.1. Visit Windows, Phase Definitions and Baseline

Figure 1: Schematic Overview of the Study

Phases will be constructed as follows:

Trial phase	Start date	End date
Screening (phase 0)	00:00 of the date of signing the informed consent form	1 minute before the first study medication intake
Treatment (phase 1)	Datetime of first study medication intake	Datetime of last study medication intake + 72 hours
Follow-up (phase 2)	End of the phase 1 +1 minute	23:59 of trial termination date (date of last contact).

The last phase, whichever it is for a subject, always ends on 23:59 of the day of trial termination (last contact).

Events will be assigned to phases based on their datetime, but seconds will be ignored overall. If the daypart of the start date of the event is present but the timepart is missing, the event will be treated as if it started at 00:00 on the day of the event. If the daypart of the end date of the event is present but the timepart is missing, the event will be treated as if it happened at 23:59 on the day of the event.

The number of days in the study (*reldy*) will be defined as:

$$reldy = visit\ day - reference\ day + 1$$

for visits on or after the reference day, and

$$reldy = visit\ day - reference\ day$$

for visits before the reference, where the reference day equals the start date of the treatment phase.

All scheduled assessments after first administration of trial medication will be used. Unscheduled assessments post-dose will not be used in descriptive statistics or any per-time point analysis, but will be used in the determination of the worst-case per treatment, and in listings as applicable.

For assessments on day 1 to 6 and for daily assessments after day 6, the numeric analysis visits (AVISITN) will be equal to the relday.

For assessments on Day 7, Day 10, Day 14 and Day 28, the following table will be used to allocate analysis time points:

Target Day	Analysis time point (numeric version)	Analysis time point	Time interval (days)
7	7	Day 7	[7,9]
10	10	Day 10	[10,12*]
14	14	Day 14	[12*,16]
28	28	Day 28	[17,+∞[
For Katz ADL, DLCO and Spirometry, vital signs and physical examination in outpatients, 12-lead ECG, Mid-tubinate nasal swabs, blood sampling for hematology and biochemistry			
* Depending on the VISIT label, subjects returning on Day 12 should be assigned to Day 10 or Day 14			

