4.3.2. Clinical Laboratory Tests

Laboratory parameters of hematology, serum chemistry and urinalysis will be investigated: All analyses will be done on SI-converted values as available in the database.

Unifying multiple laboratory values by standardization:

Since local labs are used, the SI-converted values will be standardized using the following formula and using the phantom laboratory generalized lab norms (GLN) as proposed by Francis Ruvuna, David Flores et al.^[13]

$$y = (x - Li) * \frac{Ucs - Lcs}{Ui - Li} + Lcs$$

Where

y = the transformed individual analyte value to a common standard laboratory reference range;

x = the original value;

L_i and U_i = lower and upper limits of normal for individual laboratory analyte;

L_{cs} and U_{cs} =lower and upper limit for the selected common standard laboratory or phantom laboratory GLN proposed by Francis Ruvana et all. [13]

The standardized values, with the phantom laboratory GLN will be used during the analysis.

Toxicity grades and abnormalities for laboratory parameters:

Toxicity grades will be computed according to the DMID adult toxicity grading list (see attachment at the end of this document). In case different grades are available for fasted/non fasted results, the results are assumed to be taken in the condition as specified in the protocol (i.e. not necessarily according to possible remarks indicating a deviation to this). If no condition is specified in the protocol, the non-fasting gradings should be used.

In case no toxicity grades are defined for any laboratory test, then non-graded abnormalities (high/low vs. normal range) will be used instead.

The worst grade over the whole observational period (treatment) will be determined.

Treatment-emergent definition for toxicity grades and abnormalities

An abnormality (toxicity grade or abnormality based on normal ranges) will be considered treatment-emergent in a particular phase if it is worse than the baseline value. If the baseline is missing, the abnormality is always considered as treatment-emergent. A shift from “abnormally low” at reference to “abnormally high” post reference (or vice versa) is also treatment-emergent. The treatment emergent definition is applicable in both, the treatment and follow-up phase.

Special assessments:

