Additional laboratory assessments corresponding to the CRF rash-pages (if any and if applicable) will only be considered in the main analysis if they are provided by the same laboratory vendor as for the main, scheduled assessments.

Otherwise these assessments will only be listed; this also means that these assessments will not be considered in the determination of worst-case per treatment, but toxicity grades or non-graded abnormalities will anyways be determined as and if applicable.

In case of missing date or time parts:

Laboratory records with missing assessment date- or time-parts (any: day, month or year) will not be used in descriptive statistics, unless the scheduled target day or time is known and a unique phase allocation is possible taking this additional information into account. These assessments will be allocated to the correct phase using the available date(time) information, and the information on their assessment schedule. In case it is not possible to assign a unique phase (e.g. unscheduled time points), the assessment will be assigned to all possible active phases based on the available date and time information. These cases will be flagged in the respective listings.

Imputations of numerical values expressed as characters:

In case a laboratory test result is *censored* (no numeric value is available, but only a verbatim term), the following rules are applied:

- ‘<x’ or ‘>x’: a numeric value will be imputed by a value exceeding the cut-off value with one unit
- ‘≤x’ or ‘≥x’: imputation by x.

This also applies to normal limits expressed as such.

No such imputations will be done for urinalysis parameters as these are usually character/categorical expressions.

Missing normal limits:

Missing normal limits in the data base will be imputed at analysis level using the values specified and approved by the sponsor. This only applies if the missing normal limit is critical to determine a toxicity grade or an abnormality score, i.e. not for tests whose toxicity grade is based on the test value itself. Imputations, if applicable, will be flagged as applicable if shown in listings.

Derivation of GFR (CKD-EPI equation):

Estimated GFR (CKD-EPI equation) will be calculated using the following formula^[14]:

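### SAP 4.3.2 makes an unexplained exception to SAP 2.1: rash-page laboratory results from a different laboratory vendor are graded and listed but left out of the worst-grade and treatment-emergent tables.

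*SAP*

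**What the plan says.** SAP 4.3.2, under its paragraph on special assessments, states that additional laboratory results belonging to the rash pages "will only be considered in the main analysis if they are provided by the same laboratory vendor as for the main, scheduled assessments". Otherwise they are only listed, and the SAP spells out the consequence: "these assessments will not be considered in the determination of worst-case per treatment". It adds that "toxicity grades or non-graded abnormalities will anyways be determined as and if applicable", so a grade exists for these results but does not reach the table.

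The general rule is in SAP 2.1. Unscheduled post-dose assessments are kept out of descriptive statistics and per-time-point analyses, but "will be used in the determination of the worst-case per treatment".

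On laboratories, Protocol 9.7 says: "Blood samples for serum chemistry and hematology will be collected and analyzed by a local laboratory". SAP 4.3.2 takes this as its reason for rescaling: "Since local labs are used, the SI-converted values will be standardized using the following formula". It then says: "The standardized values, with the phantom laboratory GLN will be used during the analysis".

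**The concern.** A same-vendor condition makes sense when one central laboratory runs the scheduled tests and anything else is on a different footing. This trial has no such laboratory for safety haematology and chemistry. Each site uses a local laboratory, and the SAP already provides a way to put their results on one scale. The condition therefore excludes results for a reason that the rest of the same section has dealt with.

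It is also tied to why the sample was drawn. Footnote v of the Time and Events Schedule provides for collecting routine-care blood results from hospitalised subjects, and for ad hoc safety samples, with no vendor condition. Only rash-page samples carry one.

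At stake are the SAP 4.3.2 tables built on the worst value: the cross-tabulation of worst toxicity against baseline by phase, the treatment-emergent worst grades, and the cumulative counts. Leaving a result out of a maximum cannot raise it, so any error goes towards under-reporting. The primary endpoint and the type 1 error are not involved.

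**Working it through.** The plan gives no figure to reproduce. The check sets the rules side by side and then gives the scale of one omitted subject.

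**1. Which rule governs a rash-page result?** SAP 2.1 would count it towards the worst case as an unscheduled post-dose assessment. SAP 4.3.2 is specific to rash-page laboratory results and overrides that when the vendor differs.

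**2. When does the exception apply?** The SAP does not define *vendor*.
- If it means the laboratory that runs the subject's scheduled tests, a rash sample run there is included and one run elsewhere is excluded.
- If it means any laboratory serving the study sites, fewer samples are excluded.

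The two readings can give different tables, and the SAP does not choose between them.

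**3. Can such samples arise?** Protocol Attachment 7 provides for a safety blood sample in Grade 3 or 4 rash on rash Days 1 and 3 to 6, at the investigator's discretion or the dermatologist's request. It also allows further assessments at the investigator's discretion in any rash. It names no laboratory. How many samples would go to a different laboratory cannot be worked out from the documents.

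**4. Is there a technical reason to exclude them?** The SAP states none. Missing normal limits are imputed under SAP 4.3.2 when they are critical to a grade or abnormality score. Haemoglobin, neutrophils and platelets are graded on fixed thresholds in the SAP attachment. One gap remains: the standardisation formula needs each laboratory's lower and upper limits, and the imputation rule does not say that it covers this step.

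**5. Direction.** The worst grade is a maximum over a set of results. Removing results from the set leaves the maximum unchanged or lowers it.

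**6. Scale.** SAP 1.2 plans 30 subjects per regimen, and SAP 2.4 adds a pooled ALS-008176 group to the safety tables, which is 30 + 30 = 60 subjects. If one subject's only Grade 3-4 value is omitted, the tabulated incidence falls by:
- 1/30 = 3.3 percentage points in that arm;
- 1/60 = 1.7 percentage points in the pooled active group.

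**The case against.** The strongest reply is that this is a deliberate, prespecified exception with little or no reach. A specific rule that qualifies a general one is not a contradiction. The SAP hedges the rule as applying only if such samples exist, and a sample run at the subject's usual laboratory is included. That stands: a reader might infer that SAP 2.1 and 4.3.2 conflict, but 4.3.2 states its own consequence and it is clear which rule prevails.

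The values also remain visible. They are graded and listed, and SAP 4.3.2 has a separate listing for Grade 2 or higher. Protocol 9.7 requires clinically relevant laboratory changes to be recorded as adverse events, which SAP 4.3.1 summarises by toxicity grade. This also stands, so it would be wrong to say that severe toxicity disappears from the report. The adverse-event route is only a partial substitute: it depends on the investigator's judgement, and individual events are tabulated only when there are at least 5.

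A reader might go further and suppose that a dermatology referral sends the blood elsewhere, or that a Grade 4 value would be tabulated as Grade 0 or 1. The documents support neither. Attachment 7 names the dermatologist as a possible requester and says nothing of who analyses the sample. The extreme example needs every included sample to miss the toxicity, while Part 2 schedules haematology and biochemistry on Days 2, 4 and 6 in hospital and on Days 7, 10, 14 and 28. Nor do the documents show that rash samples are especially likely to reveal systemic toxicity.

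Finally, an outside laboratory may not have supplied reference ranges. Protocol 17.2.2 collects them before the first subject is enrolled, for laboratories conducting study tests. That is a plausible motive for the condition, but the SAP does not state it, and a rule for missing limits would meet it better than exclusion.

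**Conclusion.** The point holds as a minor defect in safety reporting. Followed as written, the vendor condition can keep graded rash-page results out of the worst-grade and treatment-emergent tables, for no stated reason, in a trial that uses local laboratories for these tests and standardises across them. The effect is one-sided.

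The number of subjects affected is unknown and may be zero. Each one who is affected accounts for at most 3.3 percentage points of an arm's incidence in a given grade category, or 1.7 points in the pooled active group. These figures assume 30 treated subjects per arm and that no included result from that subject reaches the same grade. The conclusion does not rest on any claim that data are lost or that the arms would be affected differently.

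**What to change.** Delete the vendor condition and its consequence from SAP 4.3.2. State that post-baseline rash-page results enter the worst-case and treatment-emergent tables like any other unscheduled result, with the SI conversion, standardisation, grading and missing-limit imputation that the section applies to all local laboratory values. Rash samples should not be graded on a separate basis, such as each laboratory's own unstandardised limits, because that would set them apart from the values used in the rest of the analysis.

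Add one sentence saying which limits to use in the standardisation formula when an outside laboratory's range is missing, since the present imputation rule covers only limits critical to a grade or abnormality score.

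The cost is a short text edit before database lock, plus obtaining or imputing reference limits for any outside laboratory. No new samples are needed and trial conduct does not change. If the sponsor prefers to keep the exception, the SAP should define *vendor* and give the reason.

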4.3.3. Vital Signs

Systolic and Diastolic blood pressure, pulse rate, respiratory rate, tympanic temperature and oxygen saturation will be investigated.

Definitions

The following abnormalities will be defined:

Abnormality Code	Vital Signs parameter		
	Pulse	DBP	SBP
Abnormalities on actual values			
Abnormally low	< 45 bpm	≤ 50 mmHg	≤ 90 mmHg
Grade 1 or mild	-	> 90 mmHg - < 100 mmHg	> 140 mmHg - < 160 mmHg
Grade 2 or moderate	-	≥ 100 mmHg - < 110 mmHg	≥ 160 mmHg - < 180 mmHg
Grade 3 or severe	-	≥ 110 mmHg	≥ 180 mmHg
Abnormally high	≥ 120 bpm	-	-

Abnormality Code	Respiratory
Abnormalities on actual values	
Normal	< 17 breaths per minute

Abnormality Code	Respiratory
Grade 1 or mild	17-20 breaths per minute
Grade 2 or moderate	21-25 breaths per minute
Grade 3 or severe	> 25 breaths per minute
Grade 4 or potentially life threatening	intubation-

Abnormality Code	Tympanic Temperature (°C)
Abnormalities on actual values	
Normal	< 37.5
Abnormally high	≥ 37.5

Abnormality Code	Oxygen Saturation (%)
Abnormalities on actual values	
Abnormally low	< 95
Normal	≥ 95

In determining the abnormalities, the following rules are applied:

- worst grades/abnormalities are determined over the whole observational period for each trial phase separately, including post-baseline scheduled and unscheduled measurements of that phase.
- The abnormalities ‘abnormally low’ and ‘abnormally high’ /grades are considered equally important, i.e. if a subject has as well an abnormally low as an abnormally high or graded value post-baseline, both abnormalities are shown in the tables. (This means that the sum of the percentages can be more than 100%)

An abnormality will be considered treatment-emergent in a particular phase if it is worse than baseline. If baseline is missing, the abnormality is always considered as treatment-emergent. A shift from ‘abnormally low’ at baseline to ‘abnormally high’ or ‘grade ...’ post baseline (or vice versa) is also treatment-emergent.

Analysis Methods

Actual values and change from baseline will be summarized by treatment group at each scheduled time point. The number and percentage of will be shown in a cross-tabulation of the toxicity/abnormality post-baseline versus baseline at each scheduled time point.

Additionally, a cross-tabulation of the worst toxicity/abnormality versus baseline will be presented per phase (Treatment phase, Follow-up phase) and for the combination of Treatment and follow-up phase. This table will also show the number and percentage of subjects per worst toxicity/abnormality, the number and percentage of subjects per treatment-emergent worst

toxicity/abnormality and the cumulative number of subjects per treatment-emergent toxicity/abnormality or worse.

Mean \pm SE graphs over time for the actual values and changes from reference will be generated for all tests performed.

A listing of abnormal individual subject VS values will be provided.

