 - m. The Katz ADL questionnaire will be completed by the investigator/study-site personnel after interviewing the subject and the data will be entered into the eCRF by the investigator/study-site personnel. The Katz ADL questionnaire will be completed twice at screening to document retrospectively the subject's pre-RSV infection functional status (ie, prior to first signs/symptoms of RSV) and the subject's current functional status (ie, after the occurrence of RSV signs/symptoms). The Katz ADL questionnaire will be completed once daily for the entire duration of hospitalization and on Day 7, Day 10, Day 14, and Day 28 if the subject is discharged.
 - n. SpO₂ will be assessed Q4h (±30 minutes) while the subject is hospitalized through Day 7. Previous time point should be used to calculate the next measurement window. In case the last SpO₂ assessment on Day 7 was performed after 8 PM, the first SpO₂ assessment on Day 8 should be performed within 8 hours from the last SpO₂ assessment on Day 7. For subjects who remain hospitalized after Day 7, SpO₂ assessment should then continue Q8h (±1 hour) until 24 hours after the cessation of supplemental oxygen. After discharge, SpO₂ will be assessed once on Day 7, Day 10, Day 14, and Day 28.
 - o. Only to be performed if the test is available at the study site and the clinical condition of the subject allows testing as judged by the investigator.
 - p. A CPE includes all body systems, height (only at screening), and body weight; a DPE includes respiratory system, nose, ear, throat, facial and neck lymph nodes, and skin examination. A CPE will be performed at screening and Day 28 and a DPE will be performed on Days 1, 2, 7, 10, and 14. Additionally, physical examination findings performed as part of standard of care on Days 8 to 13 will also be collected.
 - q. Vital signs are defined as SBP, DBP, temperature, respiratory rate, and heart rate. Symptom-directed vital signs will also be performed when deemed appropriate by the investigator or appropriately delegated study team member. Vital signs will be assessed twice daily (preferably at the same times each day, ±30 minutes) for the entire duration of hospitalization. After discharge, vital signs will be assessed once on Day 7, Day 10, Day 14, and Day 28. Additionally, vital signs assessed as part of standard of care on Days 8 to 13 will be collected.

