Data is available from 1 Phase 1b first-in-infant study (ALS-8176-503) and 1 Phase 2b study (64041575RSV2004) in hospitalized pediatric subjects with RSV infection. The clinical phase of Study ALS-8176-503 has been completed, but the database has not yet been locked.

Seventy pediatric subjects were treated in the SAD part of Study ALS-8176-503. Fifty-three subjects received single doses of ALS-008176 up to 25 mg/kg and 17 subjects received placebo. All AEs were of mild or moderate severity, except for 1 \geq Grade 3 SAE of bacterial pneumonia which was considered unrelated to the study drug.

In the MAD part of Study ALS-8176-503, 111 pediatric subjects were treated, of which 78 received multiple doses of ALS-008176 up to a 60 mg/kg LD followed by 40 mg/kg MDs twice daily, and 33 subjects received placebo twice daily. All AEs were of mild or moderate severity, except for 6 Grade \geq 3 AEs of neutropenia (N=2 Grade 3 and N=4 Grade 4), 1 Grade 3 AE of respiratory failure, and 1 Grade 3 AE of anemia. Four SAEs were reported: lymphadenitis,

neutropenia, bronchiolitis, and respiratory failure. Only the Grade 4 SAE of neutropenia (laboratory Grade 4) reported within 17 hours after the first dose of ALS-008176 (40 mg/kg LD/20 mg/kg MD twice daily) was considered possibly related to the study drug, and resulted in premature discontinuation of the study drug after the second MD. The subject experiencing a Grade 3 SAE of respiratory failure presented also a Grade 2 bacterial pneumonia, and was discontinued from the study on Day 2.

In Study 64041575RSV2004, a Grade 4 SAE of febrile neutropenia (laboratory Grade 4) that started 1 day after the last dose of study treatment was reported in a pediatric subject. The event was considered possibly related to the study drug by the investigator.

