 - Respiratory rate, heart rate, systolic blood pressure (SBP), diastolic blood pressure (DBP), and body temperature (method should be noted in the eCRF).
 - SpO₂.
 - Level of hospital care (eg, ICU, transitional care unit, ward floor).
 - Duration of hospitalization.
 - Need for hydration, and feeding by IV catheter/nasogastric tube.
 - Functional status (Katz ADL score).

Subject Evaluation

- Evaluation of RSV disease-related signs and symptoms and additional questions about health and functioning.
- HRQoL (EQ-5D-5L).

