or vital sign measurement is scheduled for the same time point as ECG recording, the procedures should be performed in the following order: ECG(s), vital signs, SpO₂, mid-turbinate nasal swabs, blood draw.

Electrocardiograms may be repeated at the investigator's discretion to account for erroneous readings.

Clinically relevant abnormalities (as defined in [Attachment 6](#)) occurring during the study should be recorded by the investigator in the AE section of the eCRF.

Vital Signs

Temperature, heart rate, respiratory rate, SBP, and DBP (methods to be noted in the eCRF) are to be collected at the time points specified in the [Time and Events Schedule](#).

Blood pressure and heart rate measurements will be assessed with a completely automated device. Manual techniques will be used only if an automated device is not available.

Blood pressure and heart rate measurements should be preceded by at least 5 minutes of rest in a sitting or supine position and in a quiet setting without distractions (eg, television, cell phones). They should not be performed immediately following the administration of beta-mimetics or any supportive drug, which could affect the measurement.

Clinically relevant abnormalities (as defined in [Attachment 6](#)) occurring during the study should be recorded by the investigator in the AE section of the eCRF.

Physical Examination

A complete physical examination (including all body systems, height [only at screening], and body weight measurement) or a directed physical examination including respiratory system, nose, ear, throat, facial and neck lymph nodes, and skin examination will be performed at the visits indicated in the [Time and Events Schedule](#).

A skin examination includes an examination of the mucous membranes, but does not include a vaginal or rectal examination. However, if the subject develops a cutaneous reaction/rash, vaginal and rectal examinations may be done if clinically relevant.

The investigator must review the physical examination results, document this review, and record any clinically relevant changes occurring during the study in the AE section of the eCRF.

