The ECG variables that will be analyzed are heart rate, PR interval, QRS interval, QT interval, and corrected QT (QTc) interval using the following correction method: QT corrected according to Fridericia's formula (QTcF). The percentage of subjects with abnormalities as defined in [Attachment 6](#) will be tabulated.

Vital Signs

Descriptive statistics of temperature, heart rate, respiratory rate, SBP, and DBP values and changes from baseline will be summarized at each scheduled time point. The percentage of subjects with values beyond clinically important limits (as defined in [Attachment 6](#)) will be summarized.

Physical Examination

Physical examination findings will be summarized at each scheduled time point. Descriptive statistics will be calculated at baseline and for observed values and changes from baseline at each scheduled time point. Frequency tabulations of the abnormalities will be made.

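### SAP 4.3.3 limits the safety analysis of temperature to tympanic readings, although the protocol prescribes no route and SAP Table 1 expects five

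*SAP*

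**What the plan says.** SAP 4.3.3 opens the safety analysis of vital signs with "Systolic and Diastolic blood pressure, pulse rate, respiratory rate, tympanic temperature and oxygen saturation will be investigated". Its only temperature block is headed "Tympanic Temperature (°C" and has two classes: normal below 37.5 and abnormally high from 37.5 upward. The worst-abnormality tables, the treatment-emergent tables and the listing of abnormal values in that section all rest on these classes. The section also has a rule that an abnormality counts as treatment-emergent whenever the baseline is missing.

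The protocol is broader:

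- Footnote q of the Time and Events Schedule reads "Vital signs are defined as SBP, DBP, temperature, respiratory rate, and heart rate" and names no route.
- Protocol 9.7 (Vital Signs) says "Temperature, heart rate, respiratory rate, SBP, and DBP (methods to be noted in the eCRF) are to be collected".
- Protocol 9.2 likewise has "body temperature (method should be noted in the eCRF" among the clinical evaluations.
- Protocol 11.10 promises "Descriptive statistics of temperature, heart rate, respiratory rate, SBP, and DBP values and changes from baseline will be summarized", with no limit by route.

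SAP Table 1, under return to normal temperature, gives normal limits for axillary, forehead, oral, rectal and tympanic readings. It uses them for an efficacy endpoint.

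**The concern.** The data are to be collected by whatever method a site uses, and the method is recorded. The safety plan then analyses one method. That is a stated rule which leaves out collected safety data, and the SAP gives no reason for it.

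At stake is the completeness of the measured-temperature part of the safety report. Hematopoietic toxicity is a named potential risk in Protocol 9.9.4, which asks for close monitoring of hematological parameters and clinical status. Protocol 1.1 reports "a Grade 4 SAE of febrile neutropenia (laboratory Grade 4) that started 1 day after the last dose of study treatment" in a pediatric study of the same compound, judged possibly related. Measured temperature by arm is therefore a table that a safety reader will look for. SAP 2.5 also plans the complete safety output by region. If thermometer practice differs between Japan and elsewhere, which the documents do not say, those tables would differ in how much temperature data they hold.

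**Working it through.** The plan states no figure on this point, so the check is a comparison of passages.

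**Step 1: which routes each analysis covers.**

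| Route | SAP Table 1 (efficacy), normal | SAP 4.3.3 (safety), normal |
|---|---|---|
| Axillary | 36.1 to 38.0 | none given |
| Forehead | 36.1 to 38.0 | none given |
| Oral | 36.1 to 38.0 | none given |
| Rectal | 37.2 or below | none given |
| Tympanic | 37.8 or below | below 37.5 |

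The safety section covers 1 of the 5 routes that the SAP itself recognises.

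**Step 2: whether another vital-sign provision fills the gap.** Protocol 11.10 refers to Attachment 6 for clinically important limits. Attachment 6 has limits for pulse, diastolic and systolic pressure, and none for temperature. It does not help.

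**Step 3: the literal consequence.** A non-tympanic reading is not in the list of parameters to be investigated, so it enters no descriptive statistics. It has no class, so it enters no cross-tabulation against baseline, no worst-abnormality table, no treatment-emergent count and no listing of abnormal values.

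**Step 4: mixed routes within a subject.** Vital signs are taken twice daily in hospital and once at each outpatient visit (footnote q), so a change of thermometer at discharge is plausible. Take an oral reading at baseline and a tympanic reading of 37.5 or more later. If only tympanic values are analysed, baseline is missing, and the missing-baseline rule makes the later value treatment-emergent. This holds even if the subject was febrile at entry, and fever is one of the presenting signs in inclusion criterion 4.

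**Step 5: the tympanic limits.** A tympanic reading from 37.5 to 37.8 inclusive is abnormally high in SAP 4.3.3 and normal in SAP Table 1. The two passages conflict.

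**Step 6: size.** Worst abnormality is determined per subject and phase, so a subject is absent from that table only if no tympanic reading exists in the phase. Let s be the share of such subjects. With about 30 subjects per arm, the number absent is 30 × s. The documents do not give s. For assumed values of 0.25, 0.50 and 0.75 the result is 7.5, 15 and 22.5 per arm; the possible range is 0 to 30. This is a share of subjects, which is not the same as a share of readings.

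**The case against.** The strongest reply is that little depends on this table, and much of that reply stands.

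- **Fever reaches the report by other paths.** Clinically relevant changes must be recorded as adverse events (Protocol 9.7). Adverse events are summarised by preferred term and toxicity grade, with serious and grade 3-4 listings (SAP 4.3.1). Protocol Attachment 1 grades oral fever. Neutrophil counts are graded, and Grade 2 or higher values are listed (SAP 4.3.2). Fever medication has its own tables (SAP 4.1.8). None of this depends on the thermometer. A reader might infer that febrile neutropenia would go unseen; the documents do not support that. The cited case was itself reported as a serious adverse event, was pediatric and arose in another study. The adult cases in Protocol 9.9.4 are pancytopenia and severe neutropenia, without mention of fever.
- **Non-tympanic readings are classed somewhere.** SAP Table 1 does so, and time to normal temperature is analysed by arm (SAP 4.2.4.2). It would be wrong to say that such fever gets no flag anywhere. But that analysis is on the ITT-i set and does not feed the safety tables.
- **The protocol required no temperature class.** This is correct: the class is a SAP addition. The departure from Protocol 11.10 is in the descriptive statistics. The abnormality tables are a gap within the SAP.
- **The wording may be a slip.** The SAP is to be read together with the protocol (SAP 1), and display details sit in a separate specification (SAP 2.4). That could rescue the descriptive statistics. It cannot supply an abnormality class for the other routes, because no limit is given for them in the safety section.
- **Arms are not biased.** A reader might infer imbalance between arms from regional thermometer habits. Randomisation is stratified by region (Protocol 5), and nothing in the documents shows that route depends on treatment. The expected harm is lost information.

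**Conclusion.** The point holds as a minor defect in the SAP. As written, the safety analysis of temperature is narrower than the protocol's and leaves out four of the five routes that the SAP anticipates. It can also label some fevers as treatment-emergent only because the baseline was taken by another route. Separately, the SAP carries two tympanic limits that disagree between 37.5 and 37.8; the documents do not settle which is right.

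The conclusion rests on reading SAP 4.3.3 literally. It also assumes that sites do use more than one route, which is inferred from the absence of a prescribed route, the instruction to record the method, and the five routes in Table 1. If every site used tympanic thermometers, nothing would be lost. The documents give no information on the actual mix, so no particular number of subjects can be claimed. The adverse-event tables and the efficacy analysis stand as they are.

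**What to change.** Before database lock, amend SAP 4.3.3 as follows:

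1. Replace tympanic temperature with body temperature by all recorded methods.
2. Class each reading as normal or abnormal by the limits for its own route, with the sponsor's justification for those limits.
3. Combine the abnormality class over routes for the worst-abnormality and treatment-emergent tables and the listing. Do not pool raw values over routes, since the SAP sets different limits for them. Present descriptive statistics by route.
4. State how baseline and change are handled when a subject's route changes. One workable rule is to take the baseline class from whichever route was used, and to compute numerical change only within the same route. The missing-baseline rule would then apply only when no reading exists by any route.
5. Reconcile the tympanic limits in SAP 4.3.3 and SAP Table 1, or explain why safety and efficacy differ.

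A listing of fever alongside low neutrophil counts could be added, but it would be a new, optional analysis and is not needed to correct this point.

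The cost is SAP wording and minor programming. The method is already recorded in the eCRF, so no new data are needed.
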